Determine the real-world effectiveness of a regional scale up of an EBI- TXTXT- among poorly adherent racial/ethnic minority YYALH, aged 16-35 years on our primary outcomes: adherence and viral load suppression at 3-month post initiation of the intervention; and secondary outcome: retention in HIV care, at 12-months post baseline.

Aim 2

Apply the Consolidated Framework for Implementation Research (CFIR) to describe the implementation process and identify barriers and facilitators needed to be addressed; and measure implementation outcomes of the TXTXT intervention using the RE-AIM framework (Reach, Efficacy, Adoption, Implementation, Maintenance).

AIM 1: RESEARCH QUESTION AND OBJECTIVES

Aim 1: Determine the real-world effectiveness of a regional scale up of an EBI- TXTXT- among poorly adherent racial/ethnic minority YYALH, aged 16-35 years on our primary outcomes: adherence and viral load suppression at 3 months post initiation of the intervention; and secondary outcome: retention in HIV care at 12 months post baseline.

RESEARCH DESIGN

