Participants will be contacted either by phone or in-person by staff members at participating clinics using the recruitment script/screener (Appendix C). If potential participants are interested in enrolling in the study (Aim 1), staff members at participating clinics which have received Institutional Review Board (IRB) certification will conduct eligibility assessment and consent conferences with participants. Potentially eligible participants will be contacted by clinic staff who will screen them for eligibility and further consent and enroll them if eligible (Appendix C). Those individuals who are ineligible will be thanked for their time.

Lurie Children's IRB will ensure that the consent forms meet institutional and funding source standards. Lurie Children's requires that research participants review and sign an informed consent form. Participants aged 16-17 years will sign an assent form (a waiver of parental consent will be obtained prior to study start). Participants aged 16-17 years are eligible to provide assent in all participating clinics. The informed consent forms include information about the overall purpose of the study, study procedures, potential risks, potential benefits to participating for individuals and society, alternatives to participating in the study, confidentiality of data, and contact information for the site's Principal Investigator and the IRB (Appendix L). Once informed consent has been obtained, the clinic staff will have the form reviewed by a fellow team member, who will confirm that it is fully completed before it is filed in a secure location under double-lock when not in use and with restricted access during work hours and/or when unattended.

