Project staff will inform participants that they have the right to skip any questions that make them feel uncomfortable. Participants will be informed that participation is completely voluntary and that they are free to stop their involvement in the study at any time without any negative consequences. Participants can stop their text messages by replying "STOP" at any time or by calling the participating clinic to unenroll in the study. Participants will be informed of their rights to privacy and confidentiality and will be told that their answers to the survey (collected via computer-assisted self-interview [CASI]) will be kept confidential and not shared with others outside of the research staff. They will be informed that no information about them or provided by them during the research will be disclosed to others without their written permission, except if necessary to protect their rights or welfare (for example, if they are injured and need emergency care) or if required by law (i.e., child or elder abuse, harm to self or others).

Dependent on site randomization, intervention sites will sign up eligible participants to receive automated SMS messages from the DimagiCommCare platform. Participants will have the option to tailor the message content based on their own preferences and will be able to select to receive messages in English or in Spanish. The time the messages are delivered, and frequency will also be selected. Clinic staff will use the text message tailoring form to record tailored messages (Appendix D). Clinic staff will enter information from this form into the text messaging platform, and then test receipt of text messages by the participant before they complete this first intervention visit. If the participant chooses a text message that discloses their HIV status, clinic staff will guide participants into selecting a discrete message and discuss options for alternate text. Participants at control sites will receive standard of care adherence counseling but will not enroll in text messaging until their site is eligible to receive the intervention. Messages used previously include, "Have you taken your vitamins

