Retention will be facilitated through obtaining contact information for the participant during the initial stages of the enrollment process. To minimize participant and staff burden, the follow-up visits can be conducted virtually. Participants will be sent a personalized link to complete the follow-up survey via REDCap. Of note, there will not be financial reimbursement for participation in the

intervention as the goal of the project is to understand how TXTXT will work in the “real world” and inform wide scale routine implementation. Prior studies by Drs. [name], [name], and [name] with vulnerable adolescent and other marginalized populations have maintained >80% retention. We will employ best practices in participant retention including: 1) collecting extensive locator information (multiple addresses/emails, phone numbers, social media profile names, etc.); 2) identification and discussion of difficult-to-reach participants and potential solutions during weekly team meetings; and 3) maintaining flexibility with mode of follow-up (e.g., in person options as well as internet based). The investigative team and participating clinic staff will review the study team’s retention plans and will be asked for guidance on how to best keep YYALH engaged in the study for at least 6 months. No financial incentives will be provided to youth participating in the TXTXT intervention trial (Aim 1). At 3 months, 6 months, and 12 months post baseline, electronic medical record (EMR) data from participating clinics will be used to determine viral load; retention in care will be assessed for up to 12 months post baseline.

STUDY DESIGN AND DATA ANALYSIS

Study participation summary

1. 12 participating clinics randomized 1:1 into intervention or comparison arm
2. 50 participants at each clinic enrolled and complete baseline survey; baseline EMR data pulled
3. Participants at intervention clinics begin TXTXT after baseline survey and continue for 6 months
4. All participants complete a 3-month survey
5. Participants at comparison clinics begin TXTXT after 3-month survey and continue for 3 months
6. All participants complete a 6-month survey; 6-month EMR data pulled
7. TXTXT intervention stops at 6 months post baseline for all participants
8. 12-month EMR data pulled

Timepoint	Who	What	Data collected
zero	12 participating clinics	Randomized 1:1 intervention: comparison arm	

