In order to assess feasibility, acceptability and satisfaction of the intervention we will use descriptive statistics using a combination of objective (e.g., rates of participation, intervention completion) and subjective measures (e.g., reported satisfaction, acceptability). In order to characterize adherence and retention in care throughout the course of the study, Kaplan-Meier survival curves will be used to measure time to adherence and retention, and Cox proportional hazard ratios will be used to assess whether individual-level factors are associated with shorter mean time to outcome. To measure reach of the intended participants, we will compare the study sample to those available in the sampling frame (proportion of those enrolled to those eligible). To measure adoption of clinic partners, we will evaluate the number of clinic partners who propose to continue with text messaging as adherence support post study (proportion of clinics who propose to continue TXTXT post study to total clinics). Satisfaction and acceptability will be measured by standard quantitative scales, summary total scores will be evaluated to determine whether or not ≥90% ratings were achieved.

Outcome definitions

Medication adherence: greater than or equal to 90% on self-reported visual analog scaler (non-adherence categorized at less than 90%)

Retention in care³³: two visits 90 days apart in the past year will be considered retained in HIV care

Viral suppression³⁴: VL < 200 copies/mL will be considered virally suppressed

Sample size, power calculation, and clinic scale up

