APPENDIX C Eligibility Screener (Aim 1)

ELIGIBILITY SCREENING INTERVIEW

SCREENING DATE: _____
Month _____ Day _____ Year _____

STAFF INITIALS: _____ **SCREENING PHASE:** In Person | Phone
(Circle one)

Hi, My name is (name) and I'm one of the staff members working on the Midwest Treatment Text (TXTXT) project, which is being conducted in partnership with Midwest AIDS Education and Training Center (MATEC) and Lurie Children's Hospital of Chicago. This project will explore whether daily text message reminders can help adolescents and young adults living with HIV do a better job of taking their medications and staying in HIV care. Are you interested in hearing more about it?

Response: If yes, continue. If no, thank them for their time and discontinue screening.

Thanks for your interest in our project. As I just said, the purpose of the study is to explore whether daily text message reminders can help adolescents and young adults living with HIV do a better job of taking their medications.

If you are eligible and decide to enroll you will be asked to provide your cell phone number and to create a text message reminder for yourself. This personalized reminder will be sent to you daily, at a time that you decide. You will be asked to text back when you take your medications. You will also continue to meet with your medical provider. Additionally, we'll ask you to complete a computer-based questionnaire at your first visit. We'll also ask you to fill out the questionnaire again at 3 months and 6 months. You will be able to complete the survey online if you prefer you can also come into the clinic site to fill out the computer survey.

If you are eligible and decide to participate, we will keep all information we collect from you strictly confidential. We will need to ask you for contact information so that we can invite you back for various stages of the intervention.

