7. Aside from eligibility criteria, does the volunteer appear to be a good fit for the project? Yes
 No (*Check ineligible and briefly explain below*) Ineligible

INSTRUCTIONS: If any of the above ineligible boxes are checked, read the INELIGIBLE script. If none of the ineligible boxes are checked, read the ELIGIBLE script below.

SCRIPT FOR INELIGIBLE VOLUNTEERS:

Participants for this project are selected based on the questions you were just asked. Based on your answers, it turns out you're not eligible to participate. Thank you for taking the time to talk with me about our project.

SCRIPT FOR ELIGIBLE VOLUNTEERS:

Thank you very much for the information you provided. Based on your answers to these questions, you are eligible to participate in this project. That means that if you want to participate in the text message project, you may. Do you think you might be interested in taking part in this project?

Response: If "NO", thank them for their time. If "YES":

Before we go any further, I need to get your name and birthdate, then schedule an appointment with you.

Participant Name*: _____ Date of Birth*: _____

Month Day Year

CONFIRM AGE GIVEN WITH DOB

* With the completion of this box, this document now contains confidential identifying information and should be securely filed with other confidential identifying records for this participant (e.g., Contact Information Sheet, Consent/Assent Form).

RECRUITER INITIALS: _____ **SCREENING DATE:** _____
Month Day Year

What's a good time for you to come in? _____ at _____ : _____ AM /PM

And if we miss you at that time, what's a good way to contact you to follow up? Phone:

What's your cell phone provider? _____

Ok to leave a voicemail message?

Just as a reminder, we need you to bring your cell phone with you to the visit because if you are randomly chosen to receive texts, we will test the text message system with your phone.

Email:

Ok to email?

Investigator/Designee

Signature

Print Name

Date

Entered into screening database

Screening ID: _____

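### The one recruitment script for all clinics promises daily texts and implies individual random selection; neither matches a design in which whole clinics are randomised and comparison participants wait 3 months

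*Combined protocol and SAP*

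**What the plan says.** Under Aim 1, Procedures for Recruitment and Informed Consent, staff at participating clinics contact candidates with the Appendix C script. The documents show one such script.

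- **Opening of the script.** A person who enrols will give a phone number and create a reminder, and "This personalized reminder will be sent to you daily, at a time that you decide". The statement has no condition and no start date.
- **Closing of the script, for eligible volunteers.** They should bring their phone because "if you are randomly chosen to receive texts, we will test the text message system with your phone".
- **Design.** The Study participation summary lists "12 participating clinics randomized 1:1 into intervention or comparison arm" as the first step, ahead of participant enrolment.
- **Comparison arm.** The recruitment section says: "Participants at control sites will receive standard of care adherence counseling but will not enroll in text messaging until their site is eligible". The Study participation summary gives the timing: "Participants at comparison clinics begin TXTXT after 3-month survey and continue for 3 months".
- **Outcomes.** Aim 1 names "primary outcomes: adherence and viral load suppression at 3-month post initiation of the intervention". Adherence is defined as "greater than or equal to 90% on self-reported visual analog scaler"; viral load comes from the medical record.

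Aim 1 participants receive no payment, no blinding is described, and attrition is planned as a single 20%.

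**The concern.** A volunteer at a comparison clinic who hears the opening of this script would expect daily reminders on enrolling. The plan gives that person standard-of-care counselling until the 3-month survey, which is the primary time point. The gap between what was described and what is delivered arises in one arm only, and before the primary adherence measurement.

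Three features make this more than an editing slip. Adherence, the outcome on which the trial is powered, is self-reported by people who know whether they are getting texts. There is no payment to keep a disappointed participant in the study. The plan assumes one attrition rate for both arms and, on missing data, says only that they will be examined as part of data-quality review. Loss or reporting that differed by arm could therefore enter the primary contrast without a planned way of handling it.

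The script also puts comparison-clinic staff in a difficult position: they must either read out a statement that does not hold at their clinic for 3 months or improvise, and improvising makes recruitment differ between arms.

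**Working it through.** **1. The statements side by side**

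| Source | Who gets texts | When | Unit chosen by chance |
|---|---|---|---|
| Appendix C, opening | everyone who enrols | not stated; no wait mentioned | none mentioned |
| Appendix C, closing | those randomly chosen | implied at the first visit | the individual |
| Recruitment section and Study participation summary | everyone | at baseline, or after the 3-month survey | the clinic |

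The first two rows contradict each other, and neither matches the third.

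**2. How many people are affected**

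12 clinics randomised 1:1 gives 6 comparison clinics. At up to 50 participants each, 6 × 50 = 300 of 600 may hear a description that does not hold for them before the primary time point. The random-selection sentence names the wrong unit at all 12 clinics.

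**3. The plan's own figures, reproduced first**

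Inputs from the sample size section: 6 sites per arm, 40 analysed per site, 2 measures per participant, within-site correlation 0.05, within-participant correlation 0.2, type I error 0.05 (taken as two-sided, which the plan does not state).

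- Attrition: 600 × 0.80 = 480, as stated.
- Design effect: 1 + 2 × (40 − 1) × 0.05 + (2 − 1) × 0.2 = 5.1.
- Effective observations per arm: 6 × 40 × 2 / 5.1 = 94.1.
- Power for a 20-point difference, two-proportion normal approximation with pooled variance under the null, at control rates 25/35/45/55%: 0.826 / 0.792 / 0.792 / 0.826. Table 2 gives 0.82 / 0.80 / 0.80 / 0.83.

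The power calculation is not in error on this point.

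**4. What extra comparison-arm loss would do to power**

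The plan gives no attrition by arm, so these are assumptions. The intervention arm stays at 40 per site; the comparison arm falls from 40 to the number shown, out of 50 enrolled.

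| Analysed per comparison site | Loss | Effective observations, comparison arm | Power for 20 points across the four control rates |
|---|---|---|---|
| 40 | 20% | 94.1 | 0.79 to 0.83 |
| 30 | 40% | 6 × 30 × 2 / 4.1 = 87.8 | 0.78 to 0.81 |
| 20 | 60% | 6 × 20 × 2 / 3.1 = 77.4 | 0.75 to 0.79 |

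Even heavy loss costs only about 4 points of power, because the number of sites dominates. Precision is not the issue.

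**5. Whether a direction of bias can be derived**

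Let the true comparison rate be p, with retention a among adherent and b among non-adherent participants. The observed rate is pa / [pa + (1 − p)b]. Take p = 0.35, one of the plan's values, and assumed retentions of 80% and 60%:

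- Non-adherent people leave more: 0.35 × 0.80 / (0.28 + 0.65 × 0.60) = 0.28 / 0.67 = 0.418. The comparison arm looks better than it is, which works against TXTXT.
- Adherent people leave more: 0.35 × 0.60 / (0.21 + 0.65 × 0.80) = 0.21 / 0.73 = 0.288. The comparison arm looks worse, which favours TXTXT.

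The sign depends entirely on who leaves, and the documents say nothing about that. These two lines show only that no direction follows; they do not estimate this trial's bias.

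**The case against.** The strongest reply is that the script is incomplete on timing rather than false. It gives no start date, comparison participants do receive texts from month 3 to month 6, and the closing sentence warns that texts are not certain at the first visit. The script is also read before a consent conference, where a form covering study procedures is reviewed; that form is not in the text available and may explain clinic assignment and the wait. Waiting for texts could even encourage completion of the 3-month survey, since texts follow it. Any unblinded waitlist design carries some risk of differential loss.

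Much of this stands, and it rules out several stronger readings that a reader might infer:

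- **That comparison participants are promised something they never get.** The texts are delayed, not denied.
- **That the trial is biased against TXTXT by a stated number of points.** Any such number needs invented drop-out inputs, and the sign can go either way.
- **That the whole primary comparison rests on self-report.** Viral suppression is also primary and comes from records; survey answers cannot colour it, although a missing viral load could still matter.
- **That participants enrol uninformed.** This cannot be judged without the consent form.
- **That people at intervention clinics are harmed by the random-selection sentence.** It names the wrong unit, but they start texts at baseline.

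What does not stand is leaving the wording alone. A warning phrased as individual chance does not tell a volunteer at a comparison clinic that texts begin about 3 months later, and a consent form that did so would then contradict what was said at screening.

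**Conclusion.** The point holds as an inconsistency with a plausible statistical consequence. The Appendix C script contradicts itself and the design, and up to 300 of 600 participants are given an inaccurate expectation for the period up to the primary comparison. That is certain from the text, provided the script is read as written at comparison clinics; the documents contain no other version.

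The resulting risk of arm-specific drop-out, or of response bias in self-reported adherence, is real and avoidable, but its size and direction are unknown. It depends on how participants react, on who leaves and on what the consent form says. No sample size or power figure needs to change. The correction is worth making before recruitment because it is cheap and because accurate recruitment information is due whether or not any bias follows.

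**What to change.** Replace both sentences in Appendix C with one script read at all 12 clinics. It should state that clinics, not individuals, are assigned by chance to start texts at enrolment or about 3 months later; that all participants complete the same surveys; and that everyone is offered texts when their clinic starts. Check that the consent and assent forms say the same.

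The script should not withhold the clinic's assignment until after consent and the baseline survey. Clinics are randomised before enrolment, so staff may already know it, and late disclosure would only move any disappointment to after enrolment.

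Two related places should be reconciled in the same edit. The general visit structure and the fidelity checklist call for the personalization form without an exception for comparison clinics. The script says daily, while the recruitment section lets participants choose frequency and the platform form offers a weekly-only option.

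The cost is a script edit, an IRB notification and possibly slightly slower enrolment once the wait is stated. Reporting enrolment and 3-month retention by arm would show whether the risk materialised.

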MATEC affiliated clinics in the Midwest region are eligible to participate in Aim 1 if meeting these criteria: (1) Clinic must have at minimum 40 current patients who are: racial/ethnic minority AND have a 'detectable' viral load AND are aged 16-35 years; (2) clinic must be willing to commit at least one staff person as lead for registering clients to receive the intervention, completing consent, and administering research surveys; (3) clinic must be willing to provide deidentified individual-level data for registered TXTXT participants, including viral load, retention in care (dates of clinic visits) at least twice per year; (4) clinic must not be using a competing medication reminder text messaging system; (5) clinic must be willing and able to rely on Lurie IRB. Once sites sign a memorandum of commitment, the study coordinator will schedule a conference call to conduct a standard of care questionnaire (Appendix K). The standard of care questionnaire will document existing clinic approaches to support adherence as well as any ancillary services (e.g., transportation assistance). This information will form a descriptive profile for each clinic.

Study Inclusion

For inclusion in the TXTXT intervention individuals must meet the following criteria: 1) diagnosed with HIV-infection and on ART regimen for at least one month (not new to ART); 2) aged 16-35 years; 3) have a viral load ≥ 200 c/mL and/or report poor adherence (<90% of pills taken in the last 30 days); 4) able to receive text messages; 5) provide informed consent for research component; and 6) are a patient of a participating clinic

Study Exclusion

Exclusion criteria includes: 1) those who are unable to give informed consent 2) those who are participating in other studies that impact primary and secondary outcomes.

Procedures for Recruitment and Informed Consent

Aim 1: Youth living with HIV (aged 16-35 years) who meet study inclusion criteria will be recruited by study staff from participating clinics. The EMR will identify potentially eligible patients who will be invited to complete further study screening and enrollment.

We will ask each clinic to construct a list of eligible patients and carefully track outreach, screening, and enrollment on an enrollment log provided. Clinics may enroll up to 50 participants (to account for 20% attrition, final sample of 40 participants per clinic).

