baseline	50 participants at each clinic	Participants at intervention clinics receive TXTXT	EMR data Baseline survey
		Participants at comparison clinics do not receive TXTXT (i.e., standard of care)	
3 months	50 participants at each clinic	Participants at intervention clinics continue with TXTXT	3-month survey
6 months	50 participants at each clinic	Participants at comparison clinics begin TXTXT TXTXT stops for all participants	EMR data 6-month survey
12 months	50 participants at each clinic		EMR data

Sampling

We will ask each clinic to construct a list of potentially eligible patients and carefully track outreach, screening, and enrollment on an enrollment log provided. Participants (N=600, n=50 per each clinic site) will be enrolled.

The list of potentially eligible patients will be constructed from available EMR data and will be queried based on: (1) diagnosed with HIV; (2) age range (16-35 years); (3) most recent viral load obtained in past 12 months. If potential participants meet the first two criteria, they will be evaluated based on (#3) viral load data. The following scenarios are possible: 1) potential participant is virally suppressed; 2) potential participant is viremic (>200 copies/mL); 3) potential participant does not have viral load data available. Patients who are viremic and meet criteria 1-3 (HIV status, age) will be considered eligible for study inclusion and will be called by clinic staff to confirm eligibility and assess interest. Patients who meet criteria 1 and 2 and are virally suppressed or missing viral load data will be contacted to assess eligibility - specifically, those who are virally suppressed will be queried about medication adherence (if <90% of pills taken in the past 30 days); for those who are missing viral load data they will be asked if they are willing to re-engage in HIV care and have labs drawn prior to enrollment (if so, they will follow steps outlined above for those with viral load

STUDY DESIGN AND DATA ANALYSIS

(VL) data). The list and eligibility assessment will be documented and reviewed on a weekly basis with individual sites to ensure timely enrollment into the study.

Data Analysis Plan and Variables

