Other language, if "other", specify _____ (*Check ineligible and continue*)

7. Do you have a cell phone that can send and receive text messages?

Yes

No (*Check ineligible and continue*)

Ineligible

RECRUITER INITIALS: _____

SCREENING DATE: _____

Month

Day

Year

8. How often would you say you use your cell phone for sending or receiving text messages?

Never (*Check ineligible and continue*)

Ineligibl

1-2 times per week

3-5 times per

week Almost

every day Every
day

Several times a day

9. Have you ever been told by a doctor or other health care provider that you have HIV infection or have AIDS?

Yes

Ineligible

No (*Check ineligible and go to ineligible script*)

10. Have you ever taken antiretroviral medications or HIV

medications? Yes

Ineligible

No (*Check ineligible and go to ineligible script*)

11. Can you tell me when you started taking antiretroviral medications or HIV medications?

≤ 1 month ago (*Check ineligible and
continue*)

Ineligibl

but ≤ 6 months ago

but ≤ 24 months ago

24 months ago

12. Are you currently participating in any other research studies or programs about HIV treatment or medication adherence (support for taking your HIV medications)?

Yes (*Check ineligible and go to ineligible script*)

Ineligible

No

13. I need to know how you are doing with taking your HIV medications. Remember that this is a study for people who are having trouble taking their meds. Please answer as honestly as you can.

1. How many medication doses would you say you missed in the past 7 days? _____ doses

2. How many medication doses would you say you missed last month?

If a) is 1 or less AND b) is less than 3, check ineligible

Ineligible

Questions 14-18 are for the interviewer only.
**DO NOT ASK THESE QUESTIONS OF THE
PARTICIPANT.**

RECRUITER INITIALS: _____ SCREENING DATE: _____
Month Day Year

3. Does the volunteer appear to speak and understand English or Spanish?
 Yes
 No (*Check ineligible and continue*) Ineligible

4. Does the volunteer appear cognitively functioning and able to understand the assent/consent process?
 Yes
 No (*Check ineligible and continue*) Ineligible

5. Does the volunteer appear visibly distraught or emotionally unstable (i.e. suicidal, manic, exhibiting violent behavior)?
 Yes (*Check ineligible and continue*) Ineligibl
eNo

6. Does the volunteer appear intoxicated or under the influence of psychoactive agents?
Yes (*Check ineligible*)
 Ineligible
 No

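### Question 13 of the eligibility screener does not implement inclusion criterion 3: it can pass virally suppressed volunteers who report taking 90% or more of their doses

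*Combined protocol and SAP*

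**What the plan says.** Study Inclusion (Aim 1), criterion 3, requires that a participant "have a viral load ≥ 200 c/mL and/or report poor adherence (<90% of pills taken in the last 30 days". Sampling spells out what this means without viremia: "those who are virally suppressed will be queried about medication adherence (if <90% of pills taken in the past 30 days". A suppressed patient therefore has one route in, adherence below 90% over 30 days.

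The recruitment section names Appendix C as the form with which clinic staff "screen them for eligibility and further consent and enroll them if eligible (Appendix C". Its Question 13 asks two counts, beginning with "How many medication doses would you say you missed in the past 7 days" and then the number missed last month. Its rule is "If a) is 1 or less AND b) is less than 3, check ineligible". The closing instruction is "If none of the ineligible boxes are checked, read the ELIGIBLE script below", and that script tells the volunteer that they are eligible. No item asks for prescribed doses per day, a percentage taken, or viral load.

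Outcome definitions sets the adherence outcome at "greater than or equal to 90% on self-reported visual analog scaler (non-adherence categorized at less than 90" percent, and counts a viral load below 200 copies/mL as suppressed.

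**The concern.** The protocol text and the form define two different populations. A count of missed doses with no denominator cannot stand in for a percentage threshold, and the 7-day count has no counterpart in criterion 3. Staff who follow the form to its end would declare eligible some suppressed volunteers whom the protocol text excludes.

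The below-90% requirement matters most for suppressed patients. They already satisfy the viral load outcome on entry, by design of the and/or in criterion 3. The adherence requirement is what ensures that one binary primary outcome is still unmet. If the form relaxes it, some participants may start the trial meeting both, and the sample drifts from the poorly adherent youth and young adults named in Aim 1. With 12 clinics randomized as units, it also matters if some sites work from the form and others from the Sampling text.

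**Working it through.** **Rule as coded.** Let a = doses missed in 7 days, b = doses missed last month, k = doses per day. Question 13 excludes only if a ≤ 1 and b < 3, so it passes anyone with a ≥ 2 or b ≥ 3. Criterion 3, for a suppressed patient, requires 1 − b/(30k) < 0.90, that is b > 3k.

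**Inputs.** The thresholds are from Question 13 and criterion 3. For k I take 1 to 3: the Appendix B training slides and the Appendix D tailoring form provide for up to three daily doses. A 30-day month follows criterion 3.

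**Reports that pass Question 13 but fail criterion 3**

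| Doses per day | Misses needed under criterion 3 | Pass on b ≥ 3, yet 90% or more taken | Pass on a = b = 2 |
|---|---|---|---|
| 1 (30 doses) | 4 or more | b = 3: 27/30 = 90.0% | 28/30 = 93.3% |
| 2 (60 doses) | 7 or more | b = 3 to 6: 57/60 = 95.0% to 54/60 = 90.0% | 58/60 = 96.7% |
| 3 (90 doses) | 10 or more | b = 3 to 9: 87/90 = 96.7% to 81/90 = 90.0% | 88/90 = 97.8% |

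**Month length.** Once daily, 3 misses is 25/28 = 89.3% over 28 days and 28/31 = 90.3% over 31, so that case depends on how last month is read. Two misses in the past week is 26/28 = 92.9% over 28 days and higher over 30 or 31, so the mismatch survives any month length.

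**Direction.** A report that Question 13 excludes on adherence has b ≤ 2, hence at least 28/30 = 93.3% taken. It therefore never turns away someone below 90%; on adherence it is only too loose.

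**How often this could occur (illustration).** Assume that each dose is missed independently. Among suppressed volunteers who pass Question 13, the share with 90% or more taken over those 30 days is:

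| True adherence | Once daily | Twice daily |
|---|---|---|
| 95% | 70% | 95% |
| 92% | 52% | 77% |
| 85% | 21% | 18% |
| 80% | 8% | 3% |
| 70% | under 1% | about 0% |

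The answer runs from almost none to almost all, depending on an adherence distribution that the documents do not give.

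**Power (illustration).** First, Table 2: design effect 1 + 2(40 − 1)(0.05) + (2 − 1)(0.2) = 5.10. Each arm has 6 × 40 × 2 = 480 observations, and 480/5.10 = 94.1 effective. A two-sided 0.05 two-proportion test at 20 points then gives 0.826, 0.792, 0.792 and 0.826, against the stated 0.82, 0.80, 0.80 and 0.83. The row is reproduced.

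Now suppose that a share f of analysed participants is adherent in both arms at 3 months whatever happens, on top of Table 2's control rates. The difference becomes 20 × (1 − f) points:

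| f | Difference | Power over the four control rates |
|---|---|---|
| 5% | 19 points | 0.75 to 0.80 |
| 10% | 18 points | 0.70 to 0.76 |
| 20% | 16 points | 0.60 to 0.69 |

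The documents give no value for f, and zero effect in this group is an assumption. These figures show sensitivity and are not an estimate of the loss.

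**The case against.** The case that this is minor has several parts.

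- **The text already states the right rule.** Sampling gives the below-90% query for suppressed patients and has eligibility assessments reviewed weekly with sites. The screener has no viral load item, so it cannot be the whole eligibility decision. This is fair, but it does not correct the form: Appendix C is the named tool, and it ends by declaring the volunteer eligible.
- **The gap is narrow once daily.** It is exactly 3 misses, or 2 in one week. The wider gaps rest on what the platform and forms allow, not on stated regimens. This stands.
- **Many enrolees may be viremic.** Each clinic must have at least 40 current minority patients aged 16 to 35 with detectable virus, and enrols up to 50. Viremic patients qualify at any adherence, and Table 2 sets control adherence at 25% to 55%, so the design never assumed a sample with no adherent members. This stands too, and limits what can be said about size.

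A reader might infer that these entrants have no room to improve and that a stated amount of power is lost. The documents do not support that. The 3-month outcome is a new visual analog report over a new 30 days, compared between arms. Under the same independent-dose assumption, once daily, the chance that a later 30-day period falls below 90% with no change in behaviour is 6% at true adherence 95%, 22% at 92% and 68% at 85%. Such participants can lapse, and preventing lapses would be a real intervention effect. The factor 20 × (1 − f) sets that effect to zero.

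**Conclusion.** The contradiction is real and rests on arithmetic alone: for one, two or three doses a day, Question 13 passes reports of 90% or more taken that criterion 3 excludes for a suppressed volunteer. It needs correcting because the form, as written, decides eligibility.

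The consequence is more modest. Such entrants lie outside the Aim 1 population. They may meet both binary primary outcomes at baseline if their visual analog score agrees with the screening answer; the two are separate reports. Their presence would tend to dilute the 3-month difference. How much depends on three things the documents do not state: the share of enrolees who are suppressed, their dosing frequency, and how their adherence is distributed. No power loss should be quoted as a finding.

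**What to change.** Reconcile Question 13 with criterion 3:

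1. Carry the EMR viral load, already compiled for the Sampling list, onto the screener.
2. Record prescribed doses per day, and reword part b) as doses missed in the last 30 days.
3. Compute percent taken = 1 − missed/(30 × doses per day).
4. For a volunteer with viral load below 200, tick ineligible when the result is 90% or more.
5. Remove the 7-day trigger.

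The viral load field is essential, because the rule branches on suppression and the form does not now record it. It also settles the converse mismatch: at present a viremic volunteer with a ≤ 1 and b < 3 is marked ineligible, although criterion 3 admits that person on viral load alone.

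The cost is two extra screener fields and a reworded rule. The downside is that somewhat fewer suppressed volunteers will qualify. No new threshold is introduced.
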